**Definitions:**

**OSA:**

Negative OSA: Patient tested and negative study obtained or Low Risk STOP BANG Assessment

Positive OSA: Patient has STOP BANG Assessment with "High Risk" result (no testing done yet)

Positive OSA: Patient tested by PSG or HST and has a positive study result of either mild, moderate, or severe OSA

**Data Analysis and Data Monitoring.**

Statistical power was calculated to detect a significant treatment effect for the desaturation primary outcome based on a chi-square goodness of fit test for the difference between the treatment and control group in the likelihood of a desaturation event. Assuming a moderate effect size for the difference between the two groups in the probability of a desaturation event (Cohen's  $w=.30$ ), a total of  $N=88$  participants ( $N=44$  per study arm) are required to achieve acceptable statistical power of 0.80 for a two-tailed test with  $\alpha=0.05$ .

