**Principal Investigator:**  
**IRB Tracking Number:** 20170730  
**Submission Notes:** There was a typo on page 5 of the WIRB document. In the section that describes the secondary rescue maneuver we mention sat> 94% which should be 90% instead as illustrated in attachments A (page 9) and B (pages 10).  
 This did not affect the results of our trial as none of our patients needed to have a secondary rescue maneuver.  
**Sponsor Name:** Bristol Hospital

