#### **End points to be measured with definitions**

Monitoring vital signs every 2-3 minutes unless there is an event:

1. O2 saturation
  - Desaturation defined as O2 sat  $\leq$  94%
  - Desaturation requiring intervention O2 sat < 90 %
2. Heart rate
3. Blood pressure
4. Respiratory rate:
  - In the control group this will be obtained from the ETCO2 monitor
  - In the treatment group this will be measured by the BiPAP machine
5. Procedure times
  - Time of start of sedation (time 0/start time)
  - Time of scope in patient
  - Time of scope out of patient
  - Time to patient opens eyes to verbal stimuli (end time) as end of procedure
6. Number of endoscope withdrawing events during procedure
7. Number of procedure cancellations after induction with propofol
8. Measure age, sex, neck circumferences, ASA score, Mallampati score, BMI and end points
9. Total dose of propofol per patient

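### Does calling the test behind the power calculation a goodness-of-fit chi-square put the sample size or the primary comparison in doubt?

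*Combined protocol and SAP*

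**What the plan says.** The only statistical text in the combined protocol and SAP is one short paragraph under Data Analysis and Data Monitoring. It says that power was "based on a chi-square goodness of fit test for the difference between the treatment and control group in the likelihood of a desaturation event". The effect is standardised: "Assuming a moderate effect size for the difference between the two groups in the probability of a desaturation event", with Cohen's w given as 0.30. The paragraph then states that 88 participants, 44 per arm, "are required to achieve acceptable statistical power of 0.80 for a two-tailed test" at alpha 0.05.

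No section says separately which test will analyse the primary outcome, whether a continuity correction applies, what happens with small expected counts, or what event risk is assumed in the control arm. The submission notes at the front, which correct a typing error about the secondary rescue threshold, say "This did not affect the results of our trial". The trial therefore had results when this version was filed.

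**The concern.** A goodness-of-fit test sets one sample against proportions fixed in advance. The paragraph describes a comparison of an event proportion between two independent groups, which is a 2x2 test of independence (or homogeneity). Taken literally, the plan powered a different design.

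The mislabelled test is also the document's only pointer to the primary analysis. With 44 per arm, the uncorrected Pearson chi-square, the continuity-corrected chi-square and Fisher's exact test can fall on opposite sides of 5%, and they do not have the same power. If the test is open, the stated 0.80 belongs to no particular analysis, and the choice could have been made after the data were seen. A standardised effect without a control risk also leaves the reader unable to judge whether the target difference was attainable.

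**Working it through.** **Inputs** (all from Data Analysis and Data Monitoring): w = 0.30, two-sided alpha 0.05, power 0.80, N = 88, 44 per arm. The documents give no event risks, so all pairs of risks with w = 0.30 were examined.

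**1. The plan's own figure.** For a 1-df chi-square the noncentrality is N × w². Power 0.80 at alpha 0.05 needs a noncentrality of 7.849.

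N = 7.849 / 0.30² = 7.849 / 0.09 = 87.2, rounded up to 88.

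Noncentral chi-square power is 0.799 at N = 87 and 0.8035 at N = 88, so the figure reproduces. Alternatives do not fit: a one-sided test needs 69, and at N = 88 power would be 0.713 with 2 df and 0.649 with 3 df. A two-cell goodness-of-fit test and a 2x2 test of independence both have 1 df and the same N × w², so the name does not affect the result.

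**2. What w = 0.30 means in two equal arms.** w = |p1 − p2| / (2 × √(p̄(1 − p̄))), where p̄ is the mean of the two risks. Three examples:
- 65% v 35%: 0.30 / (2 × √0.25) = 0.30
- 32% v 8%: 0.24 / (2 × √0.16) = 0.30
- 19% v 1%: 0.18 / (2 × √0.09) = 0.30

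**3. Exact power at 44 per arm**, enumerating all 45 × 45 possible tables:

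| Risks | Pearson, uncorrected | Continuity-corrected | Fisher's exact |
|---|---|---|---|
| 65% v 35% | 0.801 | 0.732 | 0.732 |
| 32% v 8% | 0.844 | 0.746 | 0.753 |
| 19% v 1% | 0.917 | 0.754 | 0.763 |

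Over all pairs with w = 0.30 the ranges are 0.801 to 0.947 for uncorrected Pearson, 0.732 to 0.759 for the corrected chi-square and 0.732 to 0.775 for Fisher. The stated 0.80 is met everywhere by the first and nowhere by the other two, which would need 49 per arm.

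**4. How often Pearson and Fisher disagree.** Of 1392 tables significant by Pearson, 90 are not significant by Fisher, and the reverse never occurs. The chance of landing in one of those 90 is 6.9%, 9.1% and 15.4% for the three pairs above. As an example, 13 v 5 events gives 88 × 8² / (18 × 70) = 4.47, p = 0.034 uncorrected. The continuity-corrected p is 0.064 and Fisher's is 0.062.

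**5. Type I error.** With equal risks in both arms, the exact size of uncorrected Pearson at 44 per arm is 0.059 at a 10% risk, 0.055 at 15%, 0.053 at 25% and 0.044 at 50%. Fisher's size at those risks is 0.019 to 0.026.

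**6. Control risk.** As a reduction with no events on BiPAP, w = √(p1 / (2 − p1)). Setting this to 0.30 gives p1 = 0.18 / 1.09 = 16.5%. The target is out of reach only if the control risk is below that, and nothing in the documents indicates a risk so low.

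**The case for a change.** The strongest case for a change is that the disagreement is not confined to odd tables. The 13 v 5 example is an ordinary result. A table of 5 v 0 has expected event counts of 2.5 per arm, where many analysts would switch from p = 0.021 (Pearson) to p = 0.055 (Fisher). The plan has no rule for this, results exist, and a few sentences would settle the matter without adding a patient.

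Part of this stands. The label is wrong, the chi-square is named only for power, and the continuity correction is left unstated. The match to 88 does not prove which test was run, because the same formula is commonly used whatever the final test.

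The rest does not carry a change, for three reasons.
- The shortfall in power arises only if a corrected or exact test was used. The documents mention neither, and Fisher's test is not a chi-square under any name.
- Writing uncorrected Pearson into the plan after results exist would not prespecify it. It would also install the more liberal option: all 90 discordant tables favour it, and its size passes 5% at several common event risks.
- Naming the test would still leave the comparison incomplete. The endpoint list has desaturation at 94% or lower and, separately, "Desaturation requiring intervention O2 sat < 90"%, and does not say which defines the primary event. That is a different question, and a control risk has no meaning until it is answered.

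**Conclusion.** No change to the plan is called for. Goodness of fit is a slip of terminology: N = 88 and power 0.80 (0.8035 by the noncentral chi-square) are right for the two-arm chi-square that the sentence goes on to describe. The absent analysis statement is a gap that an analyst would fill from that sentence, which already gives a chi-square, treatment against control, the likelihood of desaturation, two-sided 5% and 44 per arm.

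The remaining uncertainty is limited. If a continuity-corrected or exact test was used, power at w = 0.30 was about 0.73 to 0.78, or 2 to 7 percentage points below the stated 0.80. A reader of the trial report should note which test produced the p-value, especially if it lies near 0.05, but amending the plan after the results cannot settle that.

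Powering on a standardised effect without a control risk is sparse but legitimate. These figures assume complete data on 44 per arm and a true effect of w = 0.30. The event risks are scanned assumptions, because the documents give none.

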**Data Storage and Confidentiality**

During and after the research study the participants data will be housed in the investigator's office in a locked file cabinet and locked office after office hours. Further security will be ensured by only allowing the investigator, sub-investigator, data collection analysis, statistician and research coordinator who will have access.

**V. Risk/Benefit Assessment**

**Risk Category.** Minimal Risk

**Potential Risk.**

Risks for BiPAP use

BiPAP is commonly used and is safe. Most problems from BiPAP involve the facemask. The mask will be close fitting to allow for an air seal. Some other risks include:

- Local skin damage from the mask
- Mild stomach bloating
- Dry mouth
- Leaking from the mask, causing less pressure to be delivered
- Eye irritation
- Sinus pain or sinus congestion

Risks may differ depending on age, the amount of time BiPAP is needed, and participant medical problems.

**Alternatives to Participation.**

The participant who does not want to participate in the research study will receive the same level of care as there will be no change in the endoscopic procedure.

**vi. Subject Identification, Recruitment And Consent/Assent**

**Method of Subject Identification and Recruitment**

The prospective subjects will be identified based on the inclusion criteria and from the physician practices of [name], MD and [name], MD. The primary physician will not discuss the research or attend to recruit patients into the study. The nurse will interview, conduct patient education and obtain the consent for participation in the research study.

**Process of Consent.** [name] will obtain consent for the prospective patients. The description of the research study as stated on the consent form will be discussed with any patient who meets the inclusion criteria in the office. [name], RN will be responsible for ensuring that valid consent is obtained and documented for all subjects. Documentation of Consent forms will be entered in a tracking log and maintained in a secure area of the principal investigator's office.

**Subject Capacity.** Only patients capable of understanding and giving consent to be a participant in the research study will be included.

**Consent Form.**

**Attachment C**

**Costs to the Subject.** There is no cost to the subject for participating in this study.

**Attachment A**

DECISION TREE FOR RESEARCH STUDY

BIPAP USE DURING ENDOSCOPY

[figure not shown]
EXPERIMENTAL GROUP

DECISION TREE FOR RESEARCH STUDY

BIPAP USE DURING ENDOSCOPY

CONTROL GROUP

**Attachment C**

Reinsert  
scope

Cancel  
procedure
